5.2.2. Dose Modification Guidelines

Guidelines for reduction, hold, or permanent discontinuation of study drug are provided in [Table 1](#) (study drug related AEs) and [Table 2](#) (study drug related rash).

Table 1 Dose Modification Guidelines for Study Drug Related Adverse Events

Event	Recommended Action

Grade 2 or higher AE that is (1) study drug-related in the opinion of the Investigator AND (2) that precludes continued dosing at the current dose level due to safety concern or lack of tolerability (in the Investigator’s judgment)
	
Study Drug: May be reduced by one (1) tablet. If, in the opinion of the Investigator, a Grade 2 AE has resolved to ≤Grade 1, participant may resume study drug at the original dose. If, in the opinion of the Investigator, the AE poses a significant safety concern such that a dose hold is considered, the Investigator should contact the Medical Monitor.

ALT ≥ 3x ULN if ALT WNL at baseline OR >3X ULN AND a ≥ 2-fold increase above baseline values if elevated ALT values at baseline In the absence of additional signs of compromised liver function such as elevated PT, PTT, INR, elevated conjugated bilirubin, jaundice, or hepatic pain.
	
Study drug: Confirm by repeat testing within 48-72 hours if possible, then repeat liver panel at least weekly until ALT levels improves. Additional Actions: If ALT levels continue to increase reduce by one tablet and notify the Medical Monitor

ALT ≥5× and <8× ULN (confirmed by repeat testing within 48-72 hours) In the absence of additional signs of compromised liver function such as elevated PT, PTT, elevated conjugated bilirubin, jaundice, or hepatic pain.
	
Study drug: Reduce dose by one tablet. Additional actions: Repeat liver panel test within 48 to 72 hours if possible and then at least weekly until resolution to <5× ULN; if ALT test does not improve within 2 weeks of dose reduction, the Medical Monitor should be notified. If ALT continues to increase within 1 week after a dose reduction, dose should be interrupted and the Medical Monitor should be notified.

Dose Interruption (Hold)	
Event	Recommended Action

Grade 3 or higher AE that is (1) study drug -related in the opinion of the Investigator AND(2) that precludes continued dosing at the current or at a reduced dose level due to safety concern or lack of tolerability in the Investigator’s judgment
	
Study drug: Hold dose until ≤Grade 2, then resume study drug at original dose. If, in the opinion of the Investigator, dosing should be resumed at a lower dose, contact the Medical Monitor. If the AE recurs or worsens, reduce dose by one tablet. Maximum dose hold is 5 continuous days. If, in the opinion of the Investigator, a longer dose hold is clinically needed, the Medical Monitor should be contacted for discussion.

Drug Discontinuation	
Event	Recommended Action
Grade 3 or Higher, Study Drug-Related SAE	Study Drug: Discontinue study drug. If the Investigator considers that the participant would benefit from continuing treatment, the Medical Monitor should be contacted for discussion.
Grade 3 or higher study drug-Related AE that, at the discretion of the Investigator, warrants discontinuation of study drug (eg, has not improved or resolved after dose hold)	Study drug: Discontinue study drug 4.14. If the Investigator considers that the participant would benefit from continuing treatment, the Medical Monitor should be contacted
Consider treatment discontinuation if: 
 • ALT >8× ULN • ALT >3x ULN or 2) ALT ≥3x AND ≥ 2-fold increase above baseline values if elevated ALT values at baseline with additional signs of compromised liver function such as elevated PT, PTT, INR, elevated conjugated bilirubin, jaundice, or hepatic pain, appearance of fatigue, nausea, vomiting, right upper quadrant pain or tenderness, fever, rash, and/or eosinophilia 	Study drug: Hold dose, confirm by repeat testing within 48-72 hours if possible, and assess potential reversible causes of liver function test abnormalities. Contact the Medical Monitor for discussion of study drug discontinuation.

Table 2 Dose Modification Guidelines for Study Drug Related Rash

Dose Reduction	
Event	Recommended Action
Grade 1 or 2 Study Drug Related Rash	
Management: Consider antihistamines, topical steroids as clinically indicated.
 
Study drug: If rash does not resolve or improve to Grade 1 within 4 days after oral antihistamines and/or topical steroids, the dose may be reduced by one capsule/tablet (300 mg). The dose may be reduced further by one capsule/tablet (300 mg) if the event does not resolve.
 
If in the opinion of the Investigator, a Grade 2 AE has resolved to ≤Grade 1, participant may resume study drug at the original dose.

Dose Interruption (Hold)	
Event	Recommended Action
Grade 1 or 2 Study Drug Related Rash that Persists after Dose Reduction	
Management: Consider antihistamines, topical steroids as clinically indicated. Consider a Dermatology Consult if clinically indicated.
 
Study drug: If rash does not resolve or improve to Grade 1 on the lower dose, consider a dose hold until resolution or returns to Grade 1 or Baseline. Once rash has resolved or improved to Grade 1 dosing may be resumed at the reduced level. Maximum dose hold is 5 continuous days. If, in the opinion of the Investigator, a longer dose hold is clinically needed, the Medical Monitor should be contacted for discussion.
 
If in the opinion of the Investigator, a Grade 2 AE has resolved to Grade 1, participant may resume study drug at the original dose.

Drug Discontinuation	
Event	Recommended Action
Grade 3 or higher Study Drug Related Rash	
Study drug: Discontinue study drug
 
Consider a Dermatology Consult if clinically indicated

Abbreviations: AE = adverse event; ALT = alanine aminotransferase; SAE = serious adverse event; ULN = upper limit of normal. Participant Enrollment and Randomization

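### Table 1's ALT rules leave a confirmed 8.0× ULN without liver signs to the monitoring row, a milder action than just below or just above it, and the second ALT discontinuation bullet is malformed

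*Protocol*

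**What the plan says.** Protocol Section 5.2.2, Table 1 ("Dose Modification Guidelines for Study Drug Related Adverse Events"), has four ALT criteria.

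- **Monitoring row.** Entry is at "ALT ≥ 3x ULN if ALT WNL at baseline OR >3X ULN AND a ≥ 2-fold increase above baseline values", the second limb being for participants whose ALT was already raised at baseline. There is no upper bound. The row carries the condition "In the absence of additional signs of compromised liver function such as elevated PT, PTT, INR, elevated conjugated bilirubin, jaundice, or hepatic pain". The action is "Confirm by repeat testing within 48-72 hours if possible, then repeat liver panel at least weekly until ALT levels improves", and then "If ALT levels continue to increase reduce by one tablet and notify the Medical Monitor".
- **Reduction row.** Entry is at "ALT ≥5× and <8× ULN (confirmed by repeat testing within 48-72 hours"), again only without liver signs. The action is an immediate one-tablet reduction. Follow-up panels continue until ALT is below 5×, the Medical Monitor is told if there is no improvement in 2 weeks, and the dose is interrupted if ALT keeps rising within 1 week of the reduction.
- **First discontinuation bullet.** ALT >8× ULN, with no condition on signs or baseline.
- **Second discontinuation bullet.** "ALT >3x ULN or 2) ALT ≥3x AND ≥ 2-fold increase above baseline values if elevated ALT values at baseline with additional signs" of impaired liver function. For both bullets the action is "Hold dose, confirm by repeat testing within 48-72 hours if possible, and assess potential reversible causes of liver function test abnormalities", with Medical Monitor contact about stopping the drug.

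Section 3.2, criterion 5, excludes ALT above 4× ULN at entry.

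**The concern.** In a graded hepatic safety rule the action should not become milder as ALT rises. The reduction row stops short of 8× and the first discontinuation bullet starts above it, so the value 8.0× drops back to the monitoring row, which has no ceiling.

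The second bullet raises a related problem. It has lost part of its numbering, and its inequality signs are the reverse of the monitoring row's. A site therefore cannot be sure which participants with liver signs it is meant to catch at the 3× threshold.

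What is at stake is a consistent dosing decision for a participant at one of these values. Efficacy, power and type I error are not involved.

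**Working it through.** The plan gives no figure to reproduce. The check applies the four printed criteria at and around each boundary. ALT and baseline b are in multiples of ULN.

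**Step 1: 8.0× without signs.** Inputs are the four criteria above. "Without signs" is taken to mean none of the signs listed in any row. For a confirmed value and normal baseline:

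| ALT | ALT rows met | Strictest action |
|---|---|---|
| 3.0, 4.9 | monitoring | monitor |
| 5.0, 7.9 | monitoring, reduction | reduce now |
| 8.0 | monitoring | monitor |
| 8.1 | monitoring, first bullet | hold |

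For a raised baseline, the monitoring row also needs a 2-fold rise. Taking b ≤ 4 from the entry limit, the smallest ratio at 8.0× is 8/4 = 2.0. The condition is therefore met for every eligible baseline, and the result is the same throughout. If a 2-fold increase above baseline is taken to mean three times baseline, the condition fails when b > 8/3 = 2.67, and such a participant at 8.0× meets no ALT row at all.

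In whole-number results the gap is one reportable value: 8 × 30 = 240 U/L, 8 × 40 = 320 U/L or 8 × 50 = 400 U/L. The ULN values of 30, 40 and 50 are assumptions, because the documents give none. The share of participants affected cannot be derived.

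**Step 2: redundancy in the second bullet.** The first limb takes every ALT > 3.0 whatever the baseline. The 2-fold limb can add only ALT = 3.0, and there 3.0/b ≥ 2 requires b ≤ 3.0/2 = 1.5. If that limb is confined to raised baselines, it adds only 1 < b ≤ 1.5. On a 0.1 grid (ALT 1.0 to 20.0, b 0.3 to 4.0) this is 5 of the 4480 points that satisfy the limb.

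**Step 3: inequality signs.** The monitoring row has ≥ for a normal baseline and > for a raised one. The second bullet has > on its first limb and ≥ on the raised-baseline limb.

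**Step 4: how far the reading of the second bullet matters.**

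| Reading | 8.0×, no signs | 3.0×, normal baseline, signs |
|---|---|---|
| Signs qualify both limbs; second limb for raised baselines only | monitor | no ALT row |
| Signs qualify the second limb only | hold | no ALT row |
| Signs qualify both limbs; raised baseline governs only the 2-fold requirement | monitor | hold |

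The middle reading closes the 8.0× gap, but it would also hold the drug for every ALT > 3× without signs. That contradicts both the monitoring row and the reduction row. The 8.0× gap stands on the two readings that fit the rest of the table. The 3.0× gap does not survive the third reading.

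**The case against.** Several points on the other side are sound.

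- **The comparison at 8.0× is static.** A participant who reaches 8.0× after a confirmed 5× to <8× is already reduced, and is interrupted if ALT is still rising within a week. A reader might infer that such a participant falls back to monitoring. The follow-up attached to the reduction row does not support that. The gap is confined to someone not already reduced whose deciding repeat is exactly 8.0×.
- **The monitoring row is not passive.** It leads to a one-tablet reduction and Medical Monitor notice if ALT keeps rising.
- **There is a backstop.** The table gives recommended actions, and Section 5.2 treats modification as discretionary. Section 4.10 has clinically significant laboratory abnormalities recorded as adverse events, so the general drug-related rows allow a reduction or a hold.
- **The 3.0× gap is conditional.** A reader might infer that 3.0× with normal baseline and liver signs always meets no ALT row. The documents do not settle that. The third reading covers the case. The sign lists also differ: the second bullet adds symptoms such as nausea, fatigue, fever and rash that the lower rows do not name. A participant with only one of those could still be taken to meet the monitoring row, although the lists are given as examples.
- **The signs were read from a PDF.** The point rests on > versus ≥ and on a missing 1), so the source page should be checked. Other ≥ signs came through in the same table, so this is a caution rather than an answer.

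These points reduce the size of the problem. None of them places a confirmed 8.0× without signs in the reduction row or in the first discontinuation bullet.

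**Conclusion.** The point holds as a minor drafting defect in a safety rule. A confirmed ALT of exactly 8.0× ULN without liver signs, in a participant not already dose-reduced, gets a milder action than a confirmed 5× to <8× and a milder one than anything above 8×. This assumes that signs qualify both limbs of the second bullet, which is the only way to keep that bullet consistent with the lower rows, and that baseline ALT is at most 4× ULN.

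The second bullet is malformed and its 2-fold limb is nearly redundant. Whether it also leaves 3.0× with normal baseline and signs uncovered depends on wording whose intent the documents do not show. It would also go too far to conclude that the 2-fold limb should simply be deleted, since it is the bullet's only baseline-relative condition.

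The size is one value per boundary. No endpoint, sample size or significance level changes.

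**What to change.** 1. Change the first ALT discontinuation bullet from >8× to ≥8× ULN. This alters the action only at 8.0× without signs, because 8.0× with signs already meets the second bullet.
2. Ask the sponsor to confirm the intended wording of the second bullet, restore its numbering, and say whether the sign lists are meant to differ between rows. The result should cover any ALT ≥3× ULN with normal baseline and liver signs.
3. Leave the raised-baseline condition to clinical judgement, with both consequences in view. With no baseline condition, a participant whose ALT fell from 4× to 3.0× but who has signs would be held. With a split mirroring the monitoring row, a participant with baseline 2.0×, signs and ALT 3.1× (3.1/2.0 = 1.55) would meet no ALT row.

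The cost is an edit to two bullets of one table in an amendment, plus a site memo. No new assessments are needed, because Appendix A already schedules chemistry at the visits concerned. The cover letter says the study has completed, so the change now matters for the correctness of the plan and for any reuse of the table.

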5.3. Randomization Procedure

The randomization will be carried out centrally through an IXRS. Permuted blocks within randomization strata will be used. Eligibility should be confirmed prior to randomization on Study Day 1 (first day of dosing).

6. PARTICIPANT RANDOMIZATION

Male or female study participants with sickle cell disease (HbSC, HbSS, or HbS and HbS β^0 thal or HbS β^+ thal) who have had between 1 and 10 episodes of VOC (defined in [Section 8.1.1](#)) in the past year (the past 12 months) will be randomized within each of 3 separate study groups. Groups 1 and 2 will include 3 arms (2 voxelotor doses and placebo), Group 3 will include 2 or 3 arms (depending on voxelotor dose(s) selected for this Group).

Groups 1, 2, and 3 will be randomized in a sequential manner, as follows:

Group 1: Initially, participants will be randomized in a 1:1:1 ratio to receive oral voxelotor 900 mg, oral voxelotor 1500 mg, or matching placebo. When approximately the 60th participant reaches 12 weeks of treatment, data from the 60 participants will be unblinded for the Group 1 Analysis that will inform the dose(s) selection and other modifications for Group 3.

Group 2

Randomization into Group 2 will begin with participant #61 and will end when the Group 3 dose has been selected. It is anticipated that approximately 180 participants may be randomized, or until the doses(s) are selected for Group 3 (which ever occurs first), in a 1:1:1 ratio into Group 2.

Group 3

Randomization into Group 3 will begin after selection of the voxelotor dose(s), and completion of any necessary study design modifications. Participants will be randomized equally into dose arms to receive oral voxelotor or matching placebo. Group 3, pending Groups 1 and 2 data analysis is currently expected to enroll at least 130 participants.

6.1.1. Adolescent Participant Enrollment

A minimum of 50 adolescents will be included in the study. Refer to [Section 2.1.1](#) for information regarding enrollment of adolescent participants.

6.1.2. Stratification Factors

At the time of randomization, participants will be stratified for HU use (yes/no), geographic region (North America, Europe, Other), and age (adolescent, 12 to <18 years, and adults, 18 to 65 years).

6.2. Blinding

This study is a double-blind study. The voxelotor and placebo capsules or tablets will be matched for shape, size, and color.

With the exception of those noted below in [Section 8.3.1.1 Unblinding for Analysis](#), all individuals involved in the conduct of the study (ie, site staff and participants, Investigator, CRO

personnel, Sponsor personnel) will be blinded to randomized treatment assignment. Drug Supply personnel will remain unblinded throughout the study. Other sponsor and CRO personnel may be unblinded as required per Regulatory reporting requirements of SUSARS.

6.2.1. Events Necessitating Unblinding

Study data will be unblinded for the planned analyses. [Section 6.2.1.1](#) describes the process to support Group 1 analysis. Events that may necessitate unblinding during the conduct of the study, and specific individuals that may be unblinded to manage these events, are outlined below in [6.2.1.2](#), and [6.2.1.3](#).

6.2.1.1. Unblinding for Group 1 Analysis

To facilitate the Group 1 analyses, certain Sponsor representatives and Sponsor designees will be unblinded to treatment assignments prior to and during the data analysis (including the biostatistics contract research organization [CRO], Sponsor Biostatistics and Programming staff, and external groups for bioanalytical PK/PD). However, the rest of the Sponsor study team, including all study team members who have direct interactions with study sites, was not unblinded to individual treatment assignment. No site staff or study participants will be unblinded to randomization assignment.

6.2.1.2. Unblinding for Laboratory Test Assessment

Local laboratory tests including hematology laboratory tests may be used as needed per standard of care to manage AEs (such as hospitalization for VOC), and in these circumstances, the laboratory data may need to be unblinded.

Because knowledge of certain laboratory assessments (Hb, hematocrit [Hct], RBC count, total and unconjugated bilirubin, and absolute and % reticulocyte count) may suggest the treatment assignment, these measurements will be redacted to the Investigator and monitored on a regular basis by the DSMB. Results of redacted laboratory tests will be communicated to the Investigator if a participant's absolute reticulocyte count declines to $<80 \times 10^9/L$ or Hb declines to <5.0 g/dL or if the Hb declines ≥ 3 g/dL from screening. (but this does not require breaking of the treatment assignment blind). This is to ensure participant safety by allowing the Investigator to monitor for potential bone marrow suppression, as described in hydroxyurea (HU) monitoring guidelines (NHLBI 2014) (National Heart, Lung, and Blood Institute; NHLBI, 2014). All other laboratory assessments (not redacted) will be available to the Investigator. Anonymized laboratory results will be available to the Sponsor.

6.2.1.3. Unblinding for Medical Need

If a medical condition should arise for which appropriate treatment cannot be decided without knowledge of the treatment assignment, the Investigator may unblind a study participant. The investigator should promptly document and explain to the Sponsor any premature unblinding (eg, accidental unblinding, unblinding due to a serious adverse event) of the study participant. Pregnancy is considered a medical condition that requires unblinding. Unblinding procedures will be followed as outlined in the IWRS Manual and documented in the Investigator site file and the CRF.

7. ASSESSMENT OF SAFETY

Safety assessments will consist of recording all AEs and SAEs; protocol-specified hematology and clinical chemistry variables; measurement of protocol-specified vital signs; and the results from other protocol-specified tests that are deemed critical to the safety evaluation of voxelotor.

7.1. Data and Safety Monitoring Board

An independent DSMB will monitor the safety and conduct of the trial. The DSMB will be comprised of medical and statistical representatives. The DSMB can provide recommendations to the Sponsor regarding stopping the study or discontinuing a treatment arm or otherwise modifying the study design or conduct.

The DSMB will review:

- The Group 1 Analysis and provide an assessment of the benefit to risk ratio of the 900 mg and 1500 mg doses.
- Safety data from at least 18 adults enrolled in this study of which at least 6 adults have received 1500 mg voxelotor for at least 4 weeks to confirm acceptable safety and tolerability before adolescents can be enrolled. The sites will be notified when adolescent participants can be enrolled in this study. Additionally, this review of early safety and tolerability at 1500 mg must be satisfactory for dosing to continue to at this dose level.
- Safety data on a periodic basis as defined in the DSMB Charter.

Sites will be informed of the DSMB recommendations only if the recommendations lead to changes in the study conduct.

The composition, responsibilities, and other details of the DSMB will be described in the DSMB Charter.

8. DATA ANALYSIS AND STATISTICAL PLANS

Statistical programming and analyses will be performed using established statistical methods. Details of all planned analyses will be specified in the statistical analysis plan (SAP). The SAP will be finalized prior to study unblinding. All statistical tests will be conducted at a two sided alpha level of 0.05 unless otherwise stated.

The number of participants will be shown by visit for the duration of the treatment period. Where applicable, Baseline measurements for efficacy assessments will be the average of pre-treatment values. The study data will be reported using tables, figures, and data listings. Continuous variables will be descriptively summarized using mean, standard deviation (SD), coefficient of variation (CV%, as appropriate), median, minimum, maximum, and, as appropriate, geometric mean. Categorical variables will be descriptively summarized by presenting the number (frequency) and percentage in each category. Time to event data will be displayed as Kaplan-Meier curves. Data for participants who provide diary data, but discontinue treatment but continue in the study will be included in the analysis. Descriptive statistics for healthcare utilization will be summarized in a separate report. Where applicable, additional specifications as delineated in the SAP will supersede related descriptions in the protocol.

8.1. Endpoints

8.1.1. Primary Endpoints

The primary efficacy measure is Hb response., defined as increase of Hb from baseline by > 1 g/dL at 24 weeks. Hb at 24 weeks is determined by the average value of Hb levels at Week 20 and Week 24. If Hb assessment is missing at Week 20 or Week 24, the calculation will use the non-missing Hb level.

8.1.2. Secondary Endpoints:

The secondary efficacy endpoints are as follows:

- Change from baseline in hemoglobin at Week 24
- Change and percent change from baseline in hemolysis measures, including unconjugated bilirubin, absolute reticulocyte, reticulocytes %, and LDH at Week 24
- Incidence of severe anemic episodes (Hb < 5.5 g/dL)
- Annualized incidence rate of VOC

8.1.3. Exploratory Endpoints:

- Change from baseline in hemoglobin at Week 48 and Week 72
- Change from baseline in hemolysis measures: including unconjugated bilirubin, absolute reticulocytes, reticulocytes %, and LDH, at Week 48 and Week 72
- Time to first VOC. VOC is defined as:
 - A composite of acute painful crisis or ACS and includes the following:
 - Moderate to severe pain lasting at least 2 hours.

- No explanation other than VOC.
 - Requires oral or parenteral opioids, ketorolac, or other analgesics prescribed or directed by a healthcare professional.
 - Must be documented in patient medical record that the patient was seen, or contacted the physician, within 1 business day of the event. The event may take place in a medical setting (hospital, clinic, emergency room).
- Time to first ACS or pneumonia
 - Time to first RBC transfusion
 - Rate of opioid use as recorded in the eDiary
 - Sickle Cell Disease Severity Measure (SCDSM)
 - EuroQol EQ-5D-5L™ health questionnaire (EQ-5D-5L™)
 - Clinical Global Impression Scale (CGI)
 - School and/or work attendance as recorded via eDiary

